5.2.3 Sensitivity analyses

Analysis of the primary clinical endpoint, and relevant secondary endpoints, will be repeated with duration of organ support measured in calendar days from randomisation to the last recorded day of organ support (capped at day 30). Duration of respiratory support will be reported using Kaplan-Meier methods with time measured from randomisation to the end of the last known period of respiratory support which started on or before day 30.

Unadjusted treatment effects for the two components of the composite primary clinical endpoint (days or organ support, and mortality by day 30) will be compared to confirmed that any treatment effect is in the same direction for both components. If this appears not to be the case, the partial proportional odds model⁶ will be used to estimate adjusted treatment effects.

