2.3 Sample size

The primary clinical outcome will be analysed using rank-based methods, with death at 30 days ranked as the worst outcome. To achieve 90% power, using simulations based on data from the Oxy-PICU pilot RCT, to detect a clinically meaningful reduction in the mean duration of organ support of 12 hours from 120 to 108 hours and assuming no impact on 7.5% mortality requires a total sample size of 2040 patients (allowing for withdrawal/refusal of deferred consent of 10%).

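### Section 5.2.3 fits the partial proportional odds model only if two unadjusted effects appear to differ in direction; read as signs, that happens by chance in about 48% of trials under the sample-size scenario

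*SAP*

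**What the plan says.** SAP Section 5.2.1 fixes the primary analysis as a Wilcoxon rank-sum test, with the probabilistic index as the effect estimate. It adds ordered logistic regression, first unadjusted and then adjusted for age group, reason for admission, gas-exchange severity, predicted mortality and site (random effect).

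Section 5.2.3, on sensitivity analyses, then compares the unadjusted effects on the two components of the composite, to check that "any treatment effect is in the same direction for both components". It continues: "If this appears not to be the case, the partial proportional odds" model is to provide the adjusted effects. It gives no margin, confidence-interval criterion or test for judging direction, and no rule for a mortality difference close to zero. It does not say on what scale the effect on support days is judged, or at which cut-points the partial model is to be relaxed.

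Section 2.3 sizes the trial for a "reduction in the mean duration of organ support of 12 hours from 120 to 108 hours", "assuming no impact on 7.5% mortality".

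**The concern.** Whether a model is fitted depends on an inspection of the unblinded results, by a criterion that two analysts could apply differently. Section 1.1 says the SAP is agreed in advance so that choices of this kind are not driven by the data.

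The criterion also fits poorly with the planning scenario. If support shortens and mortality does not change, the sign of the observed mortality difference is noise, so a rule based on signs turns on chance.

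It also tests the wrong thing. Proportional odds requires the treatment odds ratio to be the same at every cut-point. Two effects can share a sign and differ greatly in size, which departs from proportional odds and still passes. At stake is whether the reader gets an adjusted ordinal analysis that separates death from support days.

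**Working it through.** **Inputs.** From Section 2.3: 2040 randomised, 10% withdrawal or refusal, 7.5% mortality in both arms, mean support 120 vs 108 hours, 90% power. From Section 2.2: 1:1 allocation. From Section 5.2.1: two-sided 5% test.

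**The plan's own figure.** 2040 × 0.90 = 1836 evaluable, or 918 per arm; in reverse, 1836 / 0.90 = 2040. The power claim itself cannot be reproduced, because it came from simulations on pilot data that the SAP does not show. A normal approximation would imply an SD of 12 / [(1.960 + 1.2816) × √(2/918)] ≈ 79 hours. The SAP does not give this value; it serves only to choose a range for the simulations below.

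**Direction of the support effect.** At 90% power the estimate favours the better arm with probability about Φ(1.960 + 1.2816) = 0.9994.

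**Direction of the mortality effect.** Deaths per arm are Binomial(918, 0.075).
- Expected deaths per arm: 918 × 0.075 = 68.85.
- SD of the difference: √(2 × 918 × 0.075 × 0.925) = 11.3 deaths.
- Exact probability of a tie: 3.5%.
- Probability of more deaths in the arm with shorter support: (1 − 0.0354) / 2 = 48.2%.
- If a tie counts as not the same direction: 48.2% + 3.5% ≈ 51.8% (unrounded).

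Because the mortality difference is symmetric about zero, 48.2% holds whichever way the support estimate points and whatever its SD. With 1020 per arm it is 48.3%. Simulations of the composite, with assumed lognormal durations (SD 70–120 hours) and gamma durations (SD 70–100 hours), 2000 runs each, judged support by the difference in survivors' mean days. They gave 47–50%.

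**If mortality truly falls in the better-support arm** (control 7.5%, 918 per arm, support direction taken as certain):

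| True mortality in that arm | Probability of opposite signs |
|---|---|
| 7.5% | 48.2% |
| 7.0% | 32.3% |
| 6.5% | 18.8% |
| 6.0% | 9.2% |
| 5.0% | 1.2% |

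**If the trigger is read strictly.** Requiring an opposite mortality difference with Fisher p < 0.05, the same simulations of the planning scenario fired in 1.6–2.3% of runs.

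**Sign agreement is not proportionality.** Take 68 deaths in the better-support arm and 69 in the other. The odds ratio for death is (68 × 849) / (69 × 850) = 57,732 / 58,650 = 0.98. Beside a clear reduction in support days, the two effects share a direction and the check passes, although there is practically no effect at the death cut-point.

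**The case against.** The case for leaving the text alone has real force on scope.

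- *The primary result is untouched.* A reader might infer that the trial's conclusion or its error rate depends on this rule. The SAP does not support that: the Wilcoxon test and probabilistic index in Section 5.2.1 are fixed whatever the signs. This stands.
- *Replacement is not stated.* A reader might infer that the adjusted common odds ratio is dropped when the trigger fires. Section 5.2.1 commits to that estimate without condition, and Section 5.2.3 does not withdraw it. An additional sensitivity model is an equally natural reading. This stands, although the SAP should say which is meant.
- *Mortality is reported anyway.* A reader might infer that a common odds ratio could hide an absent or adverse effect on death. Section 5.2.2 compares 30-day mortality by Fisher's exact test regardless. It adds adjusted logistic regression if events allow, and about 1836 × 0.075 ≈ 138 deaths are expected. Section 5.2.3 itself looks at both components every time. This largely stands.
- *The 48% assumes bare signs.* The wording leaves room for judgement, and a stricter reading gives about 2%. This stands as a limit on the figure, but the SAP chooses neither reading, and that gap is part of the problem.
- *The mortality assumption is a planning input.* It is not a prediction that the effects on death and support differ, so the 48% describes that scenario only. This stands; the table shows how quickly the figure falls.
- *A chance firing does no direct harm.* It produces the more flexible model. That is a reason to fit the model always. It does not justify leaving it to chance.

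**Conclusion.** The point holds as a defect in a supportive analysis and is worth correcting. The rule in Section 5.2.3 is undefined. On the bare-sign reading it fires by chance in about 48% of trials under the SAP's own sample-size scenario, and in about 19% if mortality in the better-support arm is truly 6.5%. On a strict reading it would fire in about 2%. On any reading it does not check proportional odds.

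The 48% rests on 918 evaluable per arm, equal mortality of 7.5%, and independence of the death counts and the support estimate. It does not rest on the unknown distribution of duration. No bias or error rate for the adjusted odds ratio has been established here, and none is claimed.

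**What to change.** In Section 5.2.3, delete the condition on direction and state that:

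- the adjusted partial proportional odds model will be fitted in every case, with the treatment effect left free at the death cut-point (score 31 against 30 or lower) and common across the support-day cut-points;
- its two odds ratios (support days; death) will be reported with 95% confidence intervals beside the adjusted common odds ratio of Section 5.2.1, whatever their directions;
- this model is additional to the Section 5.2.1 model and does not replace it.

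The unadjusted comparison of the two components can stay as description.

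The cost is a change of SAP wording and one more supportive model. That model must carry the site random effect of Section 5.2.1 and the multiple imputation of Section 5.4. This takes some programming, but the current text already calls for the same adjusted model whenever the trigger fires. No new data are needed, and the primary analysis and sample size do not change.

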5.3 Cost effectiveness analysis methods

A full cost-effectiveness analysis (CEA) will be undertaken to assess the incremental cost and net monetary benefit of the intervention, according to the intention-to-treat principle. Resource use and outcome data collected as a part of the OXY-PICU trial will be used to report cost-effectiveness at 12 months by randomised treatment group.

The cost analysis will take a health and personal health services perspective. The primary sources of the resource use data will be the OXY-PICU trial case report forms (CRFs), PICANET data, hospital episode statistics (HES) database and health service questionnaires (HSQ) on the use of personal health services which are posted to parents/guardians of surviving patients at 12 months following randomisation. Resource use data from the PICU/HDU stay will be taken from the CRF and linked to routine data from PICANet. Data on the level of care for PICU/HDU bed-days will be gathered through routine collection of the Paediatric Critical Care Minimum Dataset (PCCMDS) in the participating centres via the PICANet database. Information on subsequent PICU/HDU and hospital admissions will be obtained via data linkage with PICANet and HES database. Use of primary care and community health services will be assessed by HSQ at 12 months. Resource use data from the trial datasets, PICANet data, HES database and 12 months follow-up questionnaires will be combined with appropriate unit costs to report the total costs per patient at 12 months for both randomised groups.

Missing data in costs and HRQoL will be handled with multiple imputation, assuming the data are missing at random (MAR) conditional on the observed data (see below for details on methods used to handle missing data). On the imputed datasets the cost-effectiveness analysis will use a Bivariate Seemingly Unrelated Regression model to allow for correlation between costs and QALYs and multilevel structure of the data. We will calculate the interclass correlation coefficient (ICC) which measures the proportion of the overall variation that occurs at the cluster level . If ICC>10% we will

use multilevel models (MLM) to handle clustering and avoid potential biases and incorrect inferences. The CEA will adjust for same baseline covariates as for the analysis of primary clinical outcome to adjust for baseline imbalances between the randomised arms The incremental results from multiply-imputed datasets will summarised using Rubin's rule {Rubin, 1987 #54}.

The CEA will report the mean (95% confidence interval) incremental costs, QALYs and net monetary benefit at 12 months. Incremental costs at 30 days will also be reported. The incremental net monetary benefit (INB) of the intervention compared to control at 12 months will be calculated by multiplying the mean gain or loss in QALYs by a recommended thresholds in the UK (£20,000) and subtracting the incremental cost. The probability that the intervention is cost-effective compared to control will be presented at different levels of WTP for a QALY gain.

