1.2.1 Primary Objectives

- Composite outcome of mortality and duration of organ support at 30 days (rank-based analysis with death ranked as worse than 30 days of organ support)
- Incremental costs, quality-adjusted life years (QALYs) and net monetary benefit at 12 months

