2.2 Randomisation

Patients will be randomised on a 1:1 basis to either a liberal (>94%) or conservative (88-92%) SpO2 target, using minimisation to balance the arms with respect to age (<12 months / \geq 12 months); site; primary reason for admission (lower respiratory tract infection vs. Other); and severity of abnormality of gas exchange: SF ratio <221 with PEEP \geq 5 vs. Other.

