5.2 Clinical effectiveness analysis methods

5.2.1 Primary outcome

The primary clinical outcome will be compared between arms using a Wilcoxon rank-sum test with two-sided p-value of 0.05. The primary effect estimate will be the probabilistic index (the probability that the intervention is superior to the control for either mortality and/or duration of organ support), which will be presented with a 95% confidence interval.

Ordered logistic regression will be used firstly in a sensitivity analysis to estimate the unadjusted proportional odds ratio, and secondly to estimate the proportional odds after adjusting for the following baseline variables:

- age (<12 months / ≥12 months);
- primary reason for admission (lower respiratory tract infection vs. Other);
- severity of abnormality of gas exchange: SF ratio <221 with PEEP ≥5 vs. Other
- predicted mortality at PICU admission (measured using the PIMS 3⁴ score)
- site (as a random effect)

Subgroup analyses will be performed to test for interactions between the effect of allocated treatment group and the following baseline covariates:

- age (<12 months / ≥12 months);
- Age adjusted heart rate centile
- Haemoglobin level at admission

The interaction effect for continuous covariates (haemoglobin at admission) will be illustrated by calculating the adjusted hazard ratio within five categories at quintiles of the continuous variable. Heart rate will be corrected for age by grouping into centile bands⁵.

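### Section 5.3 is inconsistent on how site enters the cost-effectiveness model at or below an ICC of 10%; site should be included at every ICC

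*SAP*

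**What the plan says.** - **Status of the outcome.** SAP section 1.2.1 lists among the primary objectives: "Incremental costs, quality-adjusted life years (QALYs) and net monetary benefit at 12 months".
- **Allocation.** Section 2.2 randomises 1:1, "using minimisation to balance the arms with respect to age" and three further factors, one of which is site.
- **Adjustment list.** The only list of adjustment variables is in section 5.2.1. Its last entry is "site (as a random effect", with no condition attached.
- **Covariates for the economic model.** Section 5.3: "The CEA will adjust for same baseline covariates as for the analysis of primary clinical outcome".
- **Base economic model.** Section 5.3 specifies a "Bivariate Seemingly Unrelated Regression model to allow for correlation between costs and QALYs and multilevel structure of the data".
- **Gate.** Section 5.3 then has an ICC calculated. Multilevel models follow only above a threshold: "If ICC>10% we will" turn to them to handle clustering.

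**The concern.** A random effect for site is a multilevel model. At an ICC of 10% or less, the covariate sentence asks for that random effect and the gate withholds it. The sentence on the base model could reconcile the two, but it does not say how multilevel structure is handled: no fixed site effect and no clustered variance is named. The gate does not say whether its ICC belongs to costs, QALYs or net benefit, nor how a single ICC is obtained from several imputed datasets.

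Two analysts following section 5.3 could therefore fit different models to a primary objective. If the chosen model has no site term, a factor that allocation was balanced on is left in the error term, and the reported intervals and the probability of cost-effectiveness rest on standard errors that are too large.

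**Working it through.** The 10% cut is a decision rule with no derivation in the SAP, so there is no stated figure to reproduce. The check is what happens at or below the cut if no site term is fitted.

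**Inputs from the SAP.** Allocation is 1:1 and minimised on site (section 2.2). The total is 2040 with a 10% allowance for withdrawal or refused consent (section 2.3), so the analysable number is 2040 × 0.90 = 1836. The cut is ICC 0.10 (section 5.3). Tests are two-sided at 0.05 (section 3.1).

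**Assumptions.** The cluster is the site. There is no treatment-by-site interaction. No ICC value is given in the SAP, so a range is shown. The number of sites is not given either; 10, 15 and 25 were tried.

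**Step 1: standard error.** With arms balanced within site, site differences cancel from the treatment contrast, so its true variance involves only the within-site part, (1-ICC) of the total. A model without site uses the total variance. The ratio of reported to correct standard error is k = 1/sqrt(1-ICC).

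**Step 2: type I error** of a nominal 5% test is 2 × [1 - Phi(1.96 × k)].

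| ICC | k | SE too wide by | Type I error |
|---|---|---|---|
| 0.01 | 1.005 | 0.5% | 4.9% |
| 0.02 | 1.010 | 1.0% | 4.8% |
| 0.05 | 1.026 | 2.6% | 4.4% |
| 0.08 | 1.043 | 4.3% | 4.1% |
| 0.10 | 1.054 | 5.4% | 3.9% |

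**Step 3: information.** The ratio of reported to correct information is 1/k² = 1-ICC. At 0.10 that is 0.90, so the loss is 0.10 × 1836 = 184 patients' worth. The loss is in reported precision; the point estimate is hardly affected.

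**Step 4: illustrative power at ICC 0.10.** A comparison with 90% power under the correct standard error would have Phi(1.960 + 1.282 - 1.960 × 1.054) = Phi(1.176) = 88.0%. The SAP states no power for the economic outcome.

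**Step 5: simulation.** Minimisation on site and three binary factors (biased-coin probability 0.8), 1836 patients, a normal outcome and 4000 runs per setting.

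| ICC | SE without site / SE with site, over 10, 15, 25 sites |
|---|---|
| 0.02 | about 1.009 |
| 0.05 | 1.022 to 1.024 |
| 0.10 | 1.047 to 1.050 |

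At ICC 0.10, type I error was 0.040 to 0.042 without site and 0.050 to 0.054 with it. The direction is confirmed, and the size is slightly below the formula.

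**Step 6: stability of the gate.** The usual large-sample standard error of an ICC is sqrt{2(1-r)²[1+(m-1)r]² / [m(m-1)(J-1)]}, with J sites of m patients. At r = 0.10:
- J = 10, m = 183.6: about 0.045.
- J = 25, m = 73.4: about 0.03.

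For a true ICC near the cut, chance would largely decide which model is used.

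**The case against.** The strongest reply is that section 5.3 says, before the gate, that the bivariate regression is meant to allow for multilevel structure, and that the gate concerns one technique only. Site could enter both equations as a fixed covariate at every ICC, with random-effects modelling added above 10%. On that reading the sentences are compatible and the standard errors are not too wide.

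This stands in part. A reader might infer that site enters the model only above the cut, that the two instructions can never both be met, and that the economic standard errors will be too wide. The SAP does not establish any of these, because site may be handled some other way below the cut. But it does not state that other way, and the list it borrows specifies site as a random effect, which is what the gate withholds.

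A reader might also infer that the gate allows the model to be picked freely after seeing the data. It does not: the cut is a fixed number set in advance, and an ICC is not a treatment effect. What remains is that the model depends on an outcome statistic that is not fully defined.

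Two smaller replies are fair. The primary clinical test is an unadjusted Wilcoxon test, so the cross-reference is loose; yet section 5.2.1 contains only one adjustment list. And the effect is small and conservative, which is conceded.

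**Conclusion.** Section 5.3 is inconsistent on site and leaves its handling at or below the cut undefined. That conclusion rests on the text alone. The numerical consequence is conditional: if no site term is fitted there, standard errors for the primary economic outcomes are conservatively too wide, by at most about 5%. It further assumes that the cluster is the site and that there is no treatment-by-site interaction. The formula applies to costs, QALYs and net benefit separately, each with its own ICC. This is a consistency and pre-specification defect with a modest loss of reported precision; it does not threaten validity.

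**What to change.** In section 5.3:

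1. Delete the ICC>10% gate.
2. State that site is included, as a random or a fixed effect (name one), in both the cost and the QALY equation of the bivariate model, whatever the ICC.
3. Replace the general reference to multilevel structure with that named mechanism.
4. Report the ICCs for costs and QALYs as descriptive statistics only.

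The cost is SAP wording. No new data are needed, and the multilevel model is already planned as an option. The gain is one defined model for a primary objective, with intervals that reflect the balanced design at any ICC.

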5.3.1 Sensitivity analysis for cost-effectiveness

The following sensitivity analyses will be performed to check the robustness of primary CEA results at 12 months.

a. HRQoL data

Alternative mapping algorithms for converting PedsQL responses to CHU-9D scores will be explored(Lambe et al., 2018). We will also explore alternative distributional assumptions for QALYs.

b. Cost data

Because of the likely skewed distribution of costs, we will consider several distributions that can give a better fit of cost data. We will assess the implications of potential double-counting of inpatient costs across the three sources of resource data.

5.4 Handling of missing data

The amount of missing data for the survival component of the primary clinical outcome is assumed to be minimal. Patients who consent to data collection and were subsequently lost to follow-up after discharge from PICU but before 30 days are assumed to be alive at day 30 with no subsequent PICU readmissions. All patients discharged from hospital before day 30 are assumed to have survived to day 30.

Where a single day of organ support data is missing, but the patient has known to have received organ support on the previous and next day, we will assume that organ support was also received on the missing day. We will also assume that no organ support was given on the day of hospital discharge, unless otherwise recorded.

For the interim analysis, a complete case analysis will be presented (including only patients with complete data for the primary clinical endpoint, after making the above assumptions), and additional sensitivity analyses will be performed showing results under three different possible scenarios: i) on days where organ support data is missing, at least one form of support was provided if the child was known to be in a PICU, and not given otherwise (regardless of treatment allocation), ii) organ support is provided on all missing days for patients in the conservative arm and not provided for all missing days for patients in the liberal arm, and iii) organ support is not provided on all missing the conservative arm and is provided for all missing days for patients in the liberal arm.

For the final primary clinical analysis where organ support data is missing, we will assume that organ support was given if the patient was known to be located in a PICU/HDU or the location was not known, and organ support was not given if the patient was known to be located on a ward (or was

discharged from PICU/HDU to a ward). The validity of these assumptions will be explored by describing patterns of known organ support by location of care.

For the adjusted analysis, missing baseline variables will be imputed using the Multivariate Imputation using Chained Equations (MICE) algorithm, with the model including all baseline variables included in the adjusted models. The number of imputations will be determined according to level of missingness. Models will be fitted in each imputed dataset and results combined using Rubin's rules.

Patients who withdrew or withheld consent from data collection will not be included in the primary clinical endpoint analysis, but will be included in sensitivity analyses, firstly with all patients in the intervention group with missing outcomes assumed to have died by day 30, and all patients in the control group assumed to have survived with no further days of organ support, and secondly with the opposite assumptions, to give the absolute range of how much the results could change if the data were complete.

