3.3 Analysis Population

Following the intention to treat (ITT) principle, all randomised patients will be included in the analysis of the primary clinical endpoint, excluding only those where consent to access medical records was withheld or unobtainable (or were lost to follow-up before PICU discharge for any other reasons) before 30 days post randomisation.

A sensitivity analysis will be conducted in the per-protocol (PP) population, consisting of all randomised patients excluding those who were found to have breached the eligibility criteria following randomisation, and those where a clinical decision not to follow the trial treatment was recorded immediately post randomisation.

4 Trial population

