4.4 Consent

The parent/legal guardian of trial participants will be asked to consent to the study as soon appropriate and practical after randomisation (usually within 24-48 hrs of randomisation but the timing will vary according to the child's clinical situation). They may consent to any one or more of the following aspects: Trial continuation (i.e. treatment); access to medical records for ongoing data collection; completion of the parental stress questionnaire (at/around the time of consent); to receive a follow-up questionnaire at 6 months post-randomisation; sharing of anonymised data to support future research; to be contacted regarding future research participation. When consent is refused for access to medical records (regardless of whether or not consent has been given for trial continuation), all trial data collection should cease and no data linkage to PICANET or NHSDigital should be performed. Data collected by site staff directly to the trial CRF up to the point of consent refusal will be retained and used for analysis, but no events after this point will be recorded or reported on. If any data has already been obtained via linkage from PICANET or NHSDigital, this data will be deleted.

Where consent has been refused for trial continuation, but granted for access to medical records, data collection and linkage may continue and the patient may be included in the analysis as appropriate for each endpoint.

If consent is refused for access to medical records and/or trial continuation, the parental stress questionnaire may still be completed and reported on if this has been consented to.

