4.5 Withdrawal/follow-up

Once given, consent can be withdrawn at any time up to the end of the study. Data collected up to the point of non-consent or withdrawal of consent to data collection will be retained.

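### Section 5.4 removes everyone who withdrew or withheld data consent from the primary analysis with no time limit, so it conflicts with the day-30 limit in section 3.3 and drops children whose day-30 score is complete

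*SAP*

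**What the plan says.** - SAP 3.3 (Analysis Population) sets out an intention-to-treat set: "all randomised patients will be included in the analysis of the primary clinical endpoint, excluding only those where consent to access medical records was withheld". The same exclusion covers consent that could not be obtained and children lost before PICU discharge, in each case "before 30 days post randomisation".
- SAP 5.4 (Handling of missing data), last paragraph: "Patients who withdrew or withheld consent from data collection will not be included in the primary clinical endpoint analysis". No time limit is given. These children return only in two opposite extreme-case sensitivity analyses.
- SAP 4.5 (Withdrawal/follow-up): "consent can be withdrawn at any time up to the end of the study", and "Data collected up to the point of non-consent or withdrawal of consent to data collection will be retained".
- SAP 4.4 (Consent), on refusal of access to records: "Data collected by site staff directly to the trial CRF up to the point of consent refusal will be retained and used for analysis". Linked data are treated differently: "If any data has already been obtained via linkage from PICANET or NHSDigital, this data will be deleted".
- SAP 5.1.1 scores a death by day 30 as 31 and a survivor by calendar days with organ support from day 1 to day 30.

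**The concern.** Two sections define the primary analysis set, and they disagree about withdrawals after day 30. Two analysts following the plan could report different primary denominators, and the choice would fall to be made once consent status is known. Taken literally, 5.4 also discards primary outcomes that are complete and that the plan says it keeps.

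The trial is open and consent is sought after randomisation, so consent status may depend on arm and on the child's course. Excluding by consent status where the outcome is in hand brings in a post-randomisation selection that an intention-to-treat set is meant to avoid.

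**Working it through.** **The sections side by side**

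| Child | 3.3 | 5.4 | Day-30 score from retained data |
|---|---|---|---|
| Data consent withdrawn after day 30 | in | out | complete, if on the CRF |
| Records access refused before day 30, death already on the CRF | out | out | 31 |
| Records access refused before day 30, child alive at refusal | out | out | usually not derivable |
| Trial continuation refused, records access granted | in | in | available (4.4) |

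Only the first row is a contradiction between 3.3 and 5.4. In the second row the two sections agree on exclusion.

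**The plan's own figure.** Section 2.3 gives 2040 patients with a 10% allowance for withdrawal or refusal. 1836 / (1 − 0.10) = 2040, so the allowance step reproduces: 204 children, leaving 918 analysed per arm. The 90% power comes from simulations on pilot data that the SAP does not give, so it cannot be reproduced. The point does not depend on it.

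**Deaths within the allowance.** 204 × 0.075 = 15.3 over both arms, of 2040 × 0.075 = 153 in all. Assuming 2% to 10% refusal and 3.75% to 15% mortality among refusers, the range is 2040 × 0.02 × 0.0375 = 1.5 to 2040 × 0.10 × 0.15 = 30.6. These are upper bounds on known deaths, because only deaths on the CRF before refusal would be known.

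**Effect on the probabilistic index (PI).** Assume no true effect, 918 per arm and 69 deaths per arm (918 × 0.075 = 68.9). Let k children be lost from one arm only, with survivor scores otherwise alike. Then PI = 0.5 + (pB − pA)/2, with pA = 69/918 = 0.0752. The standard error is √[(2 × 918 + 1)/(12 × 918²)] = 0.0135.

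- k deaths lost, pB = (69 − k)/(918 − k). For k = 2, 4, 8, 15 the PI is 0.499, 0.498, 0.496, 0.492, or 0.07, 0.15, 0.30, 0.57 standard errors from 0.5.
- 15 survivors with typical scores lost, which is closer to late withdrawal: pB = 69/903 = 0.0764, a shift of 0.0006, or 0.05 standard errors.
- 15 children lost with any scores: the shift is at most 15 × 0.5/903 = 0.0083, or 0.62 standard errors.

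A design with 90% power targets 1.96 + 1.28 = 3.24 standard errors, so losing 15 deaths from one arm is 0.57/3.24 = 18% of the design effect, and losing 2 is about 2%.

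**Adding only known deaths to the primary set.** Let r be refusal, m mortality and f the share of refusers' deaths that are known, with early-refusing survivors unscored. Mortality in the analysed set becomes m[(1 − r) + fr] / [(1 − r) + frm]. As an assumed illustration take m = 7.5% in both arms, f = 0.5, and refusal of 12% against 8%, unrelated to outcome:

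- r = 0.12: 0.075 × 0.94 / (0.88 + 0.0045) = 7.97%
- r = 0.08: 0.075 × 0.96 / (0.92 + 0.003) = 7.80%

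Whole-child exclusion gives 7.5% in both arms under the same assumptions.

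**The case against.** The best defence is that 3.3 is the governing definition. It says the exclusions are the only ones and limits them to before day 30. Section 5.4 is about missing data, and its extreme-case analysis speaks of missing outcomes, so a child with a complete score was probably never meant to be removed. That may well be the intent, but 5.4 does not say so and has no cross-reference to 3.3. The extreme-case analyses bound the result; they do not settle who is in the primary set.

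The exposure is also limited. Under 2.7 the main analysis follows completion of day-30 follow-up, and the later update covers long-term outcomes only. Only withdrawals after a child's day 30 and before that analysis can therefore matter. This stands, and it limits the size.

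A reader might infer something stronger: that the plan improperly discards known deaths among early refusers, breaks its own intention-to-treat set, and should score those deaths as 31 in the primary analysis. The documents do not support this. Section 3.3 openly excludes consent withheld before day 30, so for those children 5.4 is consistent with it. Section 4.4 says retained CRF data are used for analysis but does not name the primary analysis, and the sensitivity analyses are one such use. Adding known deaths while survivors who refused early remain unscored selects on outcome, as the illustration shows. If refusal itself depends on outcome, whole-child exclusion is biased too, so this is a trade-off and not a plain error.

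**Conclusion.** The contradiction between 3.3 and 5.4 over withdrawals after day 30 is real and rests on the text alone. Read literally, 5.4 drops complete primary outcomes that the plan retains. It should be fixed, but the documents do not show that it threatens the trial's result.

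The SAP gives no count of late withdrawals or of known outcomes among excluded children, so the size can only be bounded. The effect on the probabilistic index is probably small: at most about 0.008 if 15 children are lost from one arm only, and about 0.0006 if they are typical survivors. These figures assume no true effect and 918 analysed per arm. The 204 children and 15 deaths are ceilings at the planning rates, across both arms and all kinds of refusal, and are not estimates of what 5.4 removes. A complete score here means one derivable from retained data, which after refusal of records access excludes linked data.

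**What to change.** 1. In 5.4, limit the exclusion to data consent withheld or withdrawn before day 30, matching 3.3, and cross-refer. State that children withdrawn after day 30 with a complete day-30 score stay in the primary analysis. Use one list of consent categories in both sections: 3.3 now names withheld or unobtainable, and 5.4 names withheld or withdrawn.
2. Apply the best-case and worst-case analyses only to children, in either arm, whose day-30 score is missing. As worded, the restriction to missing outcomes is attached to one arm only.
3. For refusals before day 30, enter outcomes already on the CRF under 4.4, including deaths scored 31, as observed values in those sensitivity analyses. Do not add the known deaths alone to the primary analysis.

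The cost is a few sentences of SAP wording, with no new data or extra patients, plus a check that the consent terms permit the use 4.4 describes. It should be settled before outcome data are inspected, as section 1.1 intends.
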